6.2.3. Analysis Methods

The main analysis method of categorical efficacy variables and health outcomes variables will use a logistic regression analysis with region, baseline disease severity (IGA), baseline value and treatment group in the model. Firth's correction will be used in order to accommodate (potential) sparse response rates. The p-value for the odds ratio from the logistic regression model will be used for statistical inference, unless Firth's correction still results in quasi-separation. In that case, Fisher's exact test will be used for statistical inference. The difference in percentages and 100(1-alpha)% CI of the difference in percentages using the Newcombe-

Wilson method without continuity correction will be reported. The p-value from the Fisher's exact test will also be produced as a secondary analysis.

The main analysis method for all continuous efficacy and health outcomes variables will use mixed model repeated measures (MMRM) analysis. The MMRM model will use a restricted maximum likelihood (REML) estimation. The model will include treatment, region, baseline disease severity (IGA), visit, and treatment-by-visit-interaction as fixed categorical effects and baseline and baseline-by-visit-interaction as fixed continuous effects. For daily diary assessments, the model for analyses up to Week 16 will include all weekly assessments. An unstructured (co)variance structure will be used to model the between- and within-patient errors. If this analysis fails to converge, the heterogeneous autoregressive [ARH(1)], followed by the heterogeneous compound symmetry (CSH), followed by the heterogeneous Toeplitz (TOEPH) will be used. The Kenward-Roger method will be used to estimate the degrees of freedom. Treatment least squares means (LSM) will be estimated within the framework of the MMRM using type 3 sums of squares. Differences in LSM between each dose of BARI and placebo (and associated p-values, standard errors and 95% CI) will be used for statistical inference. The LSM difference, standard error, p-value and 95% CI will be reported.

Treatment comparisons for continuous efficacy and health outcomes variables may also be made using analysis of covariance (ANCOVA) for primary and key secondary objectives. When an ANCOVA model is used, the model includes region, baseline disease severity, treatment group, and baseline value. Treatment LSM will be estimated within the framework of the ANCOVA using type 3 sums of squares. Reported differences in LSM and associated p-values, standard errors and 95% CI will be used for statistical inference. Treatment-by-region interaction will also be added to the model for sensitivity purposes and is discussed in Section 6.5.

Beginning on Day 14 a Cox proportional hazard (CPH) model of time (in days) to first observance of a 4-point itch reduction with effects for treatment, region, baseline mean itch, and disease severity will be used to test for treatment differences from placebo. For this analysis, daily itch scores will be compared to the baseline to determine if a 4-point itch reduction has been achieved in patients with a baseline itch of at least 4. The baseline for itch NRS is defined in Section 6.2.2. The day on which the first 4-point reduction in itch NRS is achieved will be modeled. If any significant treatment difference is observed then the same analysis will be performed on Day 13. This process of evaluating at the next lowest day will proceed until no significant differences are observed. No adjustments for multiple tests and multiple comparisons will be used. This analysis uses the Primary Censoring Rule for patients who are rescued or permanently discontinue study drug (see Section 6.4). Missing daily itch data will be replaced using NRI rule which means missing data is replaced with a non-response which would entail replacing missing values with a time to event of > 14 days, censored; >13 days, censored, etc., depending on the window being used. If the model assumptions for the CPH model do not hold, a log-rank test will be used.

Restricted mean survival time will be evaluated at Days 2, 3, 4 and 5 as an exploratory analysis. The model will include terms for baseline disease severity (IGA), baseline itch, region, and treatment group.

Fisher's exact test will be used to test for differences between each baricitinib dose and placebo in proportions of patients experiencing adverse events (AEs), discontinuation from study drug, and for other categorical safety data. Continuous vital signs, body weight, and other continuous safety variables, including laboratory variables will be analyzed by an ANCOVA with treatment group and baseline value in the model. The significance of within-treatment group changes from baseline will be evaluated by testing whether or not the treatment group LSM changes from baseline are different from zero; the standard error for the LSM change will also be displayed. Differences in LSM will be displayed, with the p-value associated with the LSM comparison to placebo and a 95% CI on the LSM difference also provided. In addition to the LSMs for each group, the within-group p-value for the change from baseline will be displayed.

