5.2. Method of Assignment to Treatment

Patients who meet all criteria for enrollment will be randomized in a 2:1:1:1 ratio (placebo, baricitinib 1-mg; baricitinib 2-mg; baricitinib 4-mg) to double-blind treatment at Visit 2 (Week 0). Randomization will be stratified by geographic region (Europe [EU], Japan [JPN], rest-of-world [ROW]) and disease severity at baseline (IGA 3 vs. 4). Assignment to treatment groups will be determined by a computer-generated random sequence using an interactive web-response system (IWRS). The IWRS will be used to assign blister packs, each containing double-blind investigational product tablets to each patient, starting at Visit 2 (Week 0), and at each visit up to and including Visit 7 (Week 12). Site personnel will confirm that they have located the correct blister packs by entering a confirmation number found on the blister packs into the IWRS.

This study will be conducted internationally in multiple sites. [Table JAHL.5.1](#) describes how regions will be defined for stratification. Regions may be combined for statistical analyses in the case when one of the region strata fails to meet the required minimum number of 30 patients. The 2 region strata with the least number of patients will then be pooled.

Table JAHL.5.1. Geographic Regions for Stratification

Region	Countries
Europe	Czech Republic, Denmark, France, Germany, Italy
Japan	Japan
Rest of World	India, Mexico, Russia, Taiwan

6. A Priori Statistical Methods

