6.3. Covariate Adjustment

The randomization to treatment groups at Week 0 (Visit 2) is stratified by disease severity (IGA) and geographic region as described in Section 5.1. Unless otherwise specified, the statistical analysis models will adjust for these stratification variables. The covariates used in the logistic model for categorical data will include the parameter value at baseline. The covariates used in the ANCOVA model for continuous data will include the parameter value at baseline. Inclusion of baseline in the model ensures treatment LSM are estimated at the same baseline value. When an MMRM analysis is performed, baseline value and baseline-by-visit interactions will be included as covariates.

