6.11.1. Primary Outcome and Methodology

The validated Investigator's Global Assessment for AD (IGA) uses the clinical characteristics of erythema, papulation/induration, oozing/crusting and lichenification to produce a single-item score ranging from 0 to 4. The primary analysis of the study is to test the null hypotheses that neither baricitinib 4-mg nor baricitinib 2-mg is superior to placebo when evaluating the proportion of patients achieving IGA of 0 or 1 at Week 16 in the ITT population. The analysis assumes that treatment response disappears after patients are rescued or permanently discontinue from treatment. This will serve as the primary estimand. In this estimand, missing data due to the application of the primary censoring rule and the occurrence of other non-censor intercurrent events will be imputed using the NRI method described in Section [6.4.1](#).

A supplemental estimand is to test the null hypotheses that neither baricitinib 4-mg nor baricitinib 2-mg is superior to placebo when evaluating the proportion of patients achieving IGA of 0 or 1 at Week 16 in the ITT population. This analysis assumes the treatment response disappears after patients permanently discontinue from treatment. In this supplemental estimand, missing data due to the application of the secondary censoring rule and the occurrence of other non-censor intercurrent events will be imputed using the NRI method described in Section [6.4.1](#).

A logistic regression analysis as described in Section [6.2.3](#) will be used for the comparisons. The odds ratio, the corresponding 95% CIs and p-value, as well as the treatment differences and the corresponding 95% CIs, will be reported.

Multiplicity controlled analyses will be performed on the primary and key secondary (see Section [4.2.1](#)) objectives to control the overall Type I error rate at a 2-sided alpha level of 0.05. A graphical approach will be used to perform the multiplicity controlled analyses as described in Section [6.6](#).

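### The interval for the primary risk difference ignores the randomisation factors that the test adjusts for: it is valid, but gives up a little precision if those factors are prognostic

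*SAP*

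**What the plan says.** Randomisation is stratified by three regions and by baseline IGA 3 or 4 (SAP 5.2, Protocol 7.2), which makes six strata.

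For categorical endpoints, SAP 6.2.3 fits a "logistic regression analysis with region, baseline disease severity (IGA), baseline value and treatment group in the model", with Firth's correction. It states that "The p-value for the odds ratio from the logistic regression model will be used for statistical inference".

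The same section then plans the effect on the percentage scale: "The difference in percentages and 100(1-alpha)% CI of the difference in percentages using the Newcombe" and "Wilson method without continuity correction will be reported". No strata, weights or standardisation are named there. SAP 6.15 names the same method for subgroups, and Protocol 10.3.1 promises only a 95% interval for the difference.

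The general rule in SAP 6.3 is: "Unless otherwise specified, the statistical analysis models will adjust for these stratification variables".

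For the primary endpoint, SAP 6.11.1 says: "The odds ratio, the corresponding 95% CIs and p-value, as well as the treatment differences and the corresponding 95% CIs, will be reported". An adjusted odds ratio with its interval is therefore already planned.

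**The concern.** The risk difference is the scale on which the trial was sized: Protocol 10.1 is powered for a 20-point absolute difference. It is also the scale most readers will take away. Yet the estimate and interval on that scale make no use of the factors within which patients are randomised.

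Severity could well predict response. Response needs a score of 0 or 1 with at least a 2-point fall, so a patient starting at IGA 3 must fall by 2 points and one starting at IGA 4 by 3. If the strata are prognostic, an interval that ignores them is wider than it need be, and it answers a slightly different question from the adjusted p-value beside it.

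The SAP is also uneven. For continuous endpoints the estimate, interval and p-value all come from one adjusted model. For the binary primary endpoint only the odds ratio and p-value do.

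**Working it through.** **1. The plan's power figure.** Inputs: 240 placebo and 120 per dose; 10% against 30% at two-sided 0.025 (Protocol 10.1).
- Pooled rate = (24 + 36)/360 = 0.1667.
- Null SE = √[0.1667 × 0.8333 × (1/240 + 1/120)] = 0.04167.
- Alternative SE = √(0.10 × 0.90/240 + 0.30 × 0.70/120) = 0.04610.
- Power = Φ[(0.20 − 2.2414 × 0.04167)/0.04610] = Φ(2.31) = 99.0%.

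With the SAP 6.1 rate of 25% for 2-mg, power is about 95% at 0.05 and 91.5% at 0.025. The stated figure of more than 90% is reproduced. It belongs to the test and does not depend on the interval.

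**2. The interval as written.** Take expected counts 24/240 and 36/120. The 95% Wilson limits are 6.8% to 14.4% and 22.5% to 38.7%.
- Lower limit = 0.20 − √[(0.300 − 0.2253)² + (0.1445 − 0.100)²] = 0.113.
- Upper limit = 0.20 + √[(0.3872 − 0.300)² + (0.100 − 0.0681)²] = 0.293.

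The difference is 20.0 points, with interval 11.3 to 29.3, about 18 points wide.

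**3. One scenario by hand (assumed inputs).** Let 60% of patients be IGA 3. Take placebo rates of 14% (IGA 3) and 4% (IGA 4), and drug rates of 33% and 13%. The overall rates are 0.6 × 14 + 0.4 × 4 = 10% and 0.6 × 33 + 0.4 × 13 = 25%, which match SAP 6.1.
- Unstratified variance = 0.10 × 0.90/240 + 0.25 × 0.75/120 = 0.0019375; SE 4.40 points.
- Stratified variance = (0.6 × 0.14 × 0.86 + 0.4 × 0.04 × 0.96)/240 + (0.6 × 0.33 × 0.67 + 0.4 × 0.13 × 0.87)/120 = 0.0018475; SE 4.30 points.
- SE ratio = 4.298/4.402 = 0.976. The half-width is 8.6 against 8.4 points.

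In simulation, the unstratified Newcombe-Wilson interval covers about 95.5% to 95.7% in this scenario, so it errs on the safe side.

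**4. A range of assumptions.** Simulated trials (1,500 or 3,000 per scenario) compared 240 with 120 patients over six strata, with 10% response on placebo and 25% or 30% on active. The IGA 4 share was 30% to 50%. Region odds ratios ran from 1/1/1 to 1/0.4/2.5. The table gives the change in 95% interval width against the unstratified interval, which averages 17.1 points (25%) to 17.9 points (30%).

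| Assumed prognosis (IGA 4 vs 3 odds ratio) | Standardised from the logistic model | Mantel-Haenszel difference |
|---|---|---|
| None to moderate (1 to 0.5) | +0.6% to −1.1% | +0.5% to −0.8% |
| Strong (0.2) | −4% to −7% | −2% to −4% |
| Extreme (0.1) | −6% to −12% | −4% to −7% |

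In the strong case, the largest saving is 7% of 17.9 = 1.25 points of total width, or about 0.6 points on each side.

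Stratified Newcombe with Mantel-Haenszel weights came out 0.1% to 1.3% wider in these runs. Other constructions and runs of it ranged from 0.3% wider to 1.7% narrower in the scenario of step 3, and one with six strata was 0.6% narrower.

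**5. Disagreement with the adjusted p-value at the same level.**
- 30% on active: at most 0.13% of trials.
- 25%: 0 to 0.9% with none to strong prognosis, 1.1% in the extreme case.
- 18%, near the significance boundary: 0.1% to 3.1%, up to 5.9% in the extreme case.

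With 1,500 trials, the Monte Carlo error on 1% is √(0.01 × 0.99/1,500) = 0.26 points. A Mantel-Haenszel interval also disagrees with the logistic p-value, in about 4% to 6% of trials at 18%. Stratifying therefore does not remove the conflict, because the test works on the odds-ratio scale.

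**6. The confidence level.** SAP 6.2.3 gives 100(1-alpha)%, SAP 6.11.1 gives 95%, and SAP 6.6 first tests each primary hypothesis at 0.025. A 95% interval set beside a test at 0.025 gives apparent conflict in 0.3% to 0.5% of trials at 30% response, 2% to 4% at 25%, and 6% to 12% at 15% to 20%. At the planned effects this exceeds the conflict from missing stratification in most scenarios.

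**The case against.** The best defence is that the risk difference is a descriptive companion. Inference rests on the adjusted odds ratio, and SAP 6.11.1 reports that ratio with its own interval, so an adjusted interval from the tested model is already there. A crude difference also has the merit of matching the percentages printed in the table. All of this stands, and it keeps the point small.

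The prognostic premise is also unsourced. The documents give no response rates by IGA 3 or 4 or by region, and no stratum sizes. That stands too: the loss can only be stated conditionally, and it may be nil.

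A reader might infer that the SAP contradicts its own rule in 6.3. It does not. That rule covers statistical models unless otherwise specified; Newcombe-Wilson is not a model, and it is specified. Nor is the primary test stratified in the strict sense: region and severity enter as main-effect covariates.

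What the defence leaves open is why the effect scale used to size the trial is the one without an adjusted estimate, when the model that would supply it is already fitted.

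**Conclusion.** The point holds as a minor matter of precision and presentation. The risk-difference interval is unadjusted while the test adjusts for region and baseline IGA. It remains valid, and is slightly conservative if those factors are prognostic. Under assumed inputs, the loss is about nil with none to moderate prognosis, roughly 2% to 7% of width with strong prognosis (4% to 7% for the model-standardised version), and up to 12% only in the extreme case.

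A reader might go further and infer that the primary conclusion is at risk, or that interval and p-value will often conflict. The documents do not support either. The decision rests on the adjusted p-value, so Type I error and power do not change. At the planned 25% to 30% response, matched-level conflict is about 1% of trials or fewer.

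These figures assume two-arm comparisons, stratum sizes fixed in proportion and a Wald p-value from the Firth model. The prognostic strengths are assumptions, not trial data.

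**What to change.** In SAP 6.2.3 and 6.11.1, add a risk difference standardised from the logistic model already specified (region, baseline IGA, baseline value, treatment). Predict each ITT patient's response probability under the dose and under placebo, average each set, take the difference, and give a delta-method interval. Keep the Newcombe-Wilson interval, labelled as unadjusted and descriptive.

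Stratified Newcombe with Mantel-Haenszel weights is not the preferred remedy. It narrows the interval little or not at all, and six strata can be sparse. SAP 5.2 pools regions only when one falls below 30 patients; a region of 30 has about 30 × 1/5 = 6 patients per active arm before the split by severity.

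In the same edit, use one confidence level throughout and say how it relates to the first test at 0.025. If 95% is kept, state that the intervals are not adjusted for multiplicity and that the p-value decides.

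The cost is a few sentences and a short program, with no new data. The drawback is that the standardised difference will not exactly equal the difference between the crude percentages shown, so the table needs a footnote.

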4.3. Exploratory Objectives

The exploratory objectives of this study are the following:

Objectives/Endpoints

• Mean change from baseline in nocturnal itch assessed by actigraphy device at 1 week and 4 weeks• Frequency of patient-reported “no itch” (Itch NRS score = 0) days from daily diaries from Week 12 to Week 16• Frequency of patient-reported “no pain” (Skin Pain NRS score = 0) days from daily diaries from Week 12 to Week 16• Mean change from baseline in the score of Item 1 of the ADSS at 1 week and 16 weeks• Mean change from baseline in the score of Item 3 of the ADSS at 1 week and 16 weeks• To evaluate changes from baseline in immunoglobulin E levels during the study• To evaluate changes from baseline in eosinophil levels during the study• To characterize baricitinib pharmacokinetics in the AD population and explore relationships between baricitinib exposure and study endpoints• To assess time to 4-pt itch reduction during the first 14 days after initiation of treatment• To assess time to improvement in Skin Pain during the first 14 days after the initiation of treatment• To assess the use of rescue therapy through the weight of sponsor provided topical corticosteroid and number of days not using rescue therapy

5. Study Design

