5.1. Summary of Study Design

Study I4V-MC-JAHL (JAHL) is a Phase 3, multicenter, randomized, double-blind, placebo-controlled, parallel-group, outpatient study evaluating the efficacy and safety of baricitinib 1-mg once daily (QD), 2-mg QD, and 4-mg QD as compared to placebo in adult patients with moderate to severe AD. The study is divided into 3 periods, a 5-week Screening period, a 16-week Double-Blinded Treatment period, and a 4-week Post-Treatment Follow-Up period. For those patients who complete the 16-week treatment period, there is an option to participate in the long-term extension study I4V-MC-JAHN (JAHN).

Approximately 600 patients ≥ 18 years of age who have responded inadequately to or who are intolerant to topical therapy will be randomized at a 2:1:1:1 ratio to receive placebo QD, baricitinib 1-mg QD, baricitinib 2-mg QD, or baricitinib 4-mg QD (240 patients in the placebo group; 120 patients in each baricitinib treatment group).

Study JAHL will consist of 3 periods:

- Period 1: Screening period is between 8 and 35 days prior to Week 0 (Visit 2)
- Period 2: Double-Blind, Placebo-Controlled Treatment period from Week 0 (Visit 2) through Week 16 (Visit 8)
- Period 3: Post-Treatment Follow-Up period from last treatment visit at Week 16 (Visit 8) or Early Termination Visit (ETV) to approximately 28 days after the last dose of investigational product

[Figure JAHL.5.1](#) illustrates the study design. The blinding procedure is described in the Protocol.

[figure not shown]

Figure JAHL.5.1. Illustration of study design for Clinical Protocol I4V-MC-JAHL.

Abbreviations: AD = atopic dermatitis; eGFR = estimated glomerular filtration rate; PPD = purified protein derivative; QD = once daily; V = visit; W = week.

- a Applicable to patients taking topical treatments (excluding emollients) or systemic treatments for AD at the time of screening.
- b For patients randomized to the 4-mg once daily dose who have renal impairment (defined as eGFR <60 mL/min/1.73 m²), the baricitinib dose will be 2-mg once daily.
- c Patients for whom PPD skin test for the evaluation of tuberculosis infection was performed at V1 must return and PPD test must be read 48 to 72 hours after Visit 1 (post-PPD).
- d Occurs approximately 28 days after the last dose of investigational product. Not required for those patients entering the long-term extension study JAHN.

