6.2. General Considerations

This plan describes *a priori* statistical analyses for efficacy, health outcomes, and safety that will be performed.

Statistical analysis of this study will be the responsibility of Eli Lilly and Company (Lilly). The statistical analyses will be performed using SAS® Version 9.4 or higher.

Not all displays described in this SAP will necessarily be included in the clinical study report (CSR). Not all displays will necessarily be created as a “static” display. Some may be incorporated into interactive display tools instead of or in addition to a static display. Any display described in this SAP and not included in the CSR will be available upon request.

Statistical tests of treatment effects and confidence intervals (CIs) will be performed at a 2-sided significance level of 0.05, unless otherwise stated (e.g., graphical multiple testing strategy in Section 6.6).

Data collected at early termination visits will be mapped to the closest scheduled visit number for that patient if it falls within the visit window as discussed in Section 6.2.2. For by-visit summaries, only visits in which a measure was scheduled to be collected will be summarized. Any unscheduled visit data will be included at the patient-level listings. However, the data will still be used in other analyses, including shift analyses for safety analytes, change from baseline using modified last observation carried forward (mLOCF) for efficacy analyses, and other categorical analyses including safety.

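### The exploratory day-by-day itch search stops only when no dose differs from placebo, so a dose that failed at Day 14 can be retested on every earlier day

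*SAP*

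**What the plan says.** The analysis serves an exploratory objective in SAP 4.3: "To assess time to 4-pt itch reduction during the first 14 days after initiation of treatment". SAP 6.2.3 gives the method: "Beginning on Day 14 a Cox proportional hazard (CPH) model of time (in days) to first observance of a 4-point itch reduction", with terms for treatment, region, baseline itch and disease severity, "in patients with a baseline itch of at least 4". A log-rank test is the fallback if the Cox assumptions fail.

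The rule for going on is "If any significant treatment difference is observed then the same analysis will be performed on Day 13". The rule for stopping is "This process of evaluating at the next lowest day will proceed until no significant differences are observed". Both refer to any treatment difference, not to the dose in question. SAP 6.2.3 then states: "No adjustments for multiple tests and multiple comparisons will be used". The level of each test is the general one in SAP 6.2: "Statistical tests of treatment effects and confidence intervals (CIs) will be performed at a 2-sided significance level of 0.05, unless otherwise stated".

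Three things are left unsaid: the lowest day to be tested, whether a dose that has failed drops out, and how an earliest day is to be read from the results.

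**The concern.** Stepping back from Day 14 and stopping at the first failure is a fixed-sequence test. For one dose against placebo it holds the error at 5% without adjustment, because a dose with no effect can reach an earlier day only by first being falsely significant at Day 14. Pooling the stopping rule over the three doses removes that protection. While one dose stays significant, the others are tested again on each earlier day whatever their own results were.

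The situation is foreseeable. Protocol 5.5 reports that in Phase 2 the 4-mg dose appeared to act faster than 2-mg on the more stringent endpoints, and it cites no Phase 2 atopic dermatitis result for 1-mg. A fast 4-mg arm could keep the search running while weaker doses are retested. A backward daily search has little use except to find the earliest day of separation, so an isolated low p-value for a weak dose could be taken as evidence of early relief that its own sequence would not have given.

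**Working it through.** **Inputs from the documents.** Two-sided 0.05 at each look (SAP 6.2). First look at Day 14 (SAP 6.2.3). Arm sizes: "240 patients in the placebo group; 120 patients in each baricitinib treatment group" (SAP 5.1).

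**Inputs that the documents do not give, assumed here.** Share with baseline itch of at least 4: 100% (240 v 120) and 85% (204 v 102). Placebo patients with a 4-point reduction by Day 14: 5%, 10%, 20% and 40%. Hazard over the 14 days: constant or rising. Hazard ratio of the dose that keeps the search going: 2, 3 or 5. The null dose has the placebo hazard. The simulations use the log-rank test, not the covariate-adjusted Cox model, with 40,000 trials per scenario.

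**1. The plan's own figure.** The SAP states no error rate for the search, only the nominal 0.05. A null dose tested at Day 14 alone is significant in 4.5% to 5.1% of simulated trials, as it should be.

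**2. Number of looks.** Day 14 back to Day 2 is 14 − 2 + 1 = 13 looks. With no lowest day stated, Day 1 is allowed, which makes 14.

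**3. Correlation between looks.** Independent looks would give 1 − 0.95^13 = 48.7%, but the looks are nested and that figure is far too high. The correlation of the test statistics at days d < d′ is about √(events by d ÷ events by d′). With events accruing evenly, this is √(7/14) = 0.71 for Days 7 and 14, and √(2/14) = 0.38 for Days 2 and 14. A Gaussian model with this correlation gives a null dose a 19.5% chance of at least one p < 0.05 over 13 looks and 22.0% over 14. The result depends on when events occur. Over 13 looks it is 14.7% if cumulative events grow as √d, 23.1% if as d^1.5 and 26.1% if as d².

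**4. Patient-level simulation, null dose tested on every day.**
- 13 looks, constant hazard: 16% to 19% (17.8% to 18.8% for placebo rates of 10% to 40%).
- 13 looks, rising hazard: 18% to 22%.
- 14 looks, both hazards: 17% to 24%.
- 13 looks, counting only differences in favour of the drug: 10% to 14%, against a nominal 2.5%.

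**5. The rule as written.** A second dose, compared with the same placebo arm, decides with the null dose whether the search continues. The floor is Day 1.

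| Hazard ratio of the other dose | Mean number of looks | Null dose significant on at least one tested day |
|---|---|---|
| 2 | 3.0 to 12.4 | 7% to 19% |
| 3 | 6.2 to 13.9 | 11% to 23% |
| 5 | 10.5 to 14.0 | 15% to 24% |

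A separate run of the full rule with 216 v 108 patients (a 90% share), constant hazard and a Day 2 floor gives 10% to 19% in either direction and 6% to 11% in favour of the drug, for hazard ratios of 2 to 5.

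**6. A separate sequence for each dose.** A null dose can gain a false day only if its Day 14 test is significant. The chance is therefore that of step 1: about 5% two-sided, or 2.5% in the drug's favour.

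**The case against.** The strongest reply is that nothing confirmatory depends on this analysis. It is listed as exploratory in SAP 4.3, and SAP 6.2.3 says openly that it is unadjusted. Early itch response is tested by dose, under family-wise control, at Weeks 1, 2 and 4 in SAP 6.6. A dose with no effect gains no controlled claim from the daily search. This stands, and it sets the weight of the point. What the disclosure does not tell a reader is that a dose which failed at Day 14 may be tested again on each earlier day.

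A second reply is that the SAP defines no onset day. If significance had to run unbroken from Day 14, the error would be about 5% even under the pooled rule. This also stands: the inflation arises only if an isolated significant day is given meaning. The text neither allows nor forbids that, which is the reason to settle it.

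A reader might infer that an ineffective dose simply has an 18% chance of a false onset day instead of 5%. The documents do not support that as a general rate. It requires another dose to stay significant back to about Day 2, it depends on an assumed event pattern, and it counts days on which the drug looks worse than placebo. The documents give no early itch effect size from which to choose a value within the range.

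**Conclusion.** The stopping rule is pooled over doses, and the result is worse than that of a step-down by dose. If another dose keeps the search going and any significant day counts as onset, an ineffective dose has roughly a 7% to 24% chance of at least one nominally significant day. The figure is about 18% when the search runs to Day 2 under a constant hazard, and about 6% to 14% when only differences in favour of the drug are counted. The comparison is about 5% two-sided, or 2.5% favourable, with separate sequences.

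The range covers constant and moderately rising hazards, hazard ratios of 2 to 5 for the other dose, placebo response of 5% to 40% by Day 14, and an 85% to 100% share with baseline itch of at least 4. All of these are assumptions. A more strongly back-loaded event pattern would give more, as the d² case shows. If no other dose is significant at Day 14, the null dose goes further only when it was itself significant, and there is no inflation.

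It would be wrong to infer that the trial's type I error control is damaged. The analysis lies outside the graphical procedure, and the primary and key secondary conclusions are unaffected. The point is minor.

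**What to change.** Add to SAP 6.2.3 that the step-down is run separately for each dose against placebo, that a dose which is not significant on a given day is not tested on any earlier day, and that the earliest day reported for a dose is the start of its unbroken run of significance from Day 14. State the lowest day to be tested.

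This holds 5% for each dose, not across the three; with all three ineffective, the chance of any false day is at most 3 × 5% = 15%. That is acceptable for an exploratory analysis, so no division of alpha is needed. No data or sample-size change follows. The cost is fewer nominal p-values for the weaker doses.
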